3.5. Visit schedule and assessments

3.5.1. Visit schedule

Examination	Screening	Pre- treatment	Q 12 Weeks	Q 24 Weeks	Q 12 months	End of study

2006-0453 Revised 4/29/2009 Page 8

Informed consent	Х					
Medical history	Х		Х		Х	Х
Concurrent medications	Х	Х	Х		Х	Х
Inclusion/exclusion criteria	Х					
Zubrod performance status	Х	Х	Х		Х	Х
Vital signs/weight	Х	Х	Х		Х	Х
Physical examination	Х	X ^b	Х		Х	Х
Pelvic exam	Х	X ^b	Х		Х	Х
ECG	Х					
CBC/DIFF/PLT		X^{b}	Х		Х	Х
Magnesium, SGOT, total bilirubin, BUN, serum creatinine, electrolytes		X ^b	X		Х	Х
Serum cholesterol		Х	Х		Х	Х
Toxicity assessment		Х	X°		$\mathbf{X}^{^{\mathrm{c}}}$	X°
CXR	Х			Х	Х	
CT scan of chest, abdomen/pelvis ^a			-	Х		

a. within 6 weeks of study entry

b. within 14 days of study entry

c. treatment-related toxicities (study drug arm)

3.5.2. Screening/Baseline

To be completed within 6 weeks of study entry

1. CT scan of the chest, abdomen/pelvis

To be completed within four weeks prior to initiation of therapy

- 1. Medical history including list of current medications and dosing schedules, history of previous therapies for current disease; and any residual toxicity from prior therapies should be recorded by using the grading schema in NCI Common Terminology Criteria for Adverse Events, Version 3.0.
- 2. Chest x-ray
- 3. ECG

To be completed within 14 days of initiation of therapy:

- 1. Weight
- 2. Complete blood count with leukocyte differential and platelet count, serum chemistries (magnesium, SGOT, total bilirubin, BUN, serum creatinine), and electrolytes.
- 3. Serum cholesterol
- 4. Vital Signs (blood pressure, pulse, respiratory rate, temperature)
- 5. Physical exam including pelvic exam
- 6. Zubrod performance status

To be obtained every 12 weeks (+/- 7 days):

- 1. Weight
- 2. Complete blood count with leukocyte differential and platelet count, serum

chemistries (magnesium, SGOT, total bilirubin, BUN, serum creatinine), electrolytes

- 3. Serum cholesterol
- 4. Vital Signs (blood pressure, pulse, respiratory rate, temperature)
- 5. Physical exam (including pelvic exam)
- 6. Zubrod performance status
- Assessment of treatment-related toxicities (study drug arm) using the grading schema in NCI Common Terminology Criteria for Adverse Events, Version 3.0.

To be obtained every 24 weeks (+/- 7 days):

- 1. Chest Xray
- 2. CT scan of the chest, abdomen and pelvis

To be obtained every 12 months (+/-7 days):

- 1. Weight
- 2. Complete blood count with leukocyte differential and platelet count, serum chemistries (magnesium, SGOT, total bilirubin, BUN, serum creatinine), electrolytes
- 3. Serum cholesterol
- 4. Vital Signs (blood pressure, pulse, respiratory rate, temperature)
- 5. Physical exam (including pelvic exam)
- 6. Zubrod performance status
- Assessment of treatment-related toxicities (study drug arm) using the grading schema in NCI Common Terminology Criteria for Adverse Events, Version 3.0.

To be obtained at the end of treatment:

- 1. Weight
- 2. Complete blood count with leukocyte differential and platelet count, serum chemistries (magnesium, SGOT, total bilirubin, BUN, serum creatinine), and electrolytes.
- 3. Serum cholesterol
- 4. Vital signs (blood pressure, pulse, respiratory rate, temperature)
- 5. Physical exam (including pelvic exam)
- 6. Zubrod performance status
- Assessment of treatment-related toxicities (study drug arm) using the grading schema in NCI Common Terminology Criteria for Adverse Events, Version 3.0.

Follow-up and further imaging:

Follow-up will be at the discretion of the patient's primary physician and based on physical findings.

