3.5.3. Safety assessments

Safety assessments will consist of monitoring and recording all adverse events and serious adverse events, the regular monitoring of hematology, blood chemistry and urine values, regular measurement of vital signs and the performance of physical examinations.

Adverse events

Information about all adverse events, whether volunteered by the subject, discovered by investigator questioning, or detected through physical examination, laboratory test or other means, will be collected and recorded. An adverse event is any undesirable sign, symptom or medical condition occurring after starting study drug (or therapy) even if the event is not considered to be related to study drug (or therapy). Study drug (or therapy) includes the drug (or therapy) under evaluation, and any reference or placebo drug (or therapy) given during any phase of the trial.

Medical conditions/diseases present before starting study treatment are only considered adverse events if they worsen after starting study treatment (any procedures specified in the protocol). Adverse events occurring before starting study treatment but after signing the informed consent form will also be recorded.

This study will utilize the Common Terminology Criteria for Adverse Events (CTCAE) version 3.0 for adverse event reporting. A copy of the CTCAE version 3.0 can be downloaded from the CTEP home page (http://www.ctep.info.nih.gov/) and is appended to this protocol. Life-threatening toxicities should be reported immediately to the Study Chairman, who in turn must notify the IRB. Reporting of adverse reactions is in addition to and does not supplant the reporting of toxicities as part of the results of the clinical trial.

This protocol will follow the Guidelines for Adverse Event Reporting appended to this protocol. In addition, the reporting requirements for Novartis are defined below.

Protocol Safety Requirements for Novartis

The principal investigator has the obligation to report all serious adverse events to the FDA, IRB, and Novartis Pharmaceuticals Clinical Safety and Epidemiology Department (CS&E).

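### Scheduled CTCAE assessments after baseline cover only treatment-related toxicity in the letrozole arm, in conflict with the all-adverse-events rule, so non-serious symptoms under observation have no scheduled grading

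*Combined protocol and SAP*

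**What the plan says.** **Scheduled assessments.** In the section 3.5.1 visit table, the toxicity row is marked after baseline at 12 weeks, 12 months and end of study. All three cells carry the footnote "c. treatment-related toxicities (study drug arm". The 12-week, 12-month and end-of-treatment lists in section 3.5.2 repeat the limit: "Assessment of treatment-related toxicities (study drug arm) using the grading schema in NCI Common Terminology Criteria for Adverse Events, Version 3.0". The pre-treatment cell has no such footnote.

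**General safety rules.** Section 3.5.3 says that "Information about all adverse events, whether volunteered by the subject, discovered by investigator questioning", or detected in other ways, will be collected and recorded, and that relatedness is not required. Its grading scale applies to all adverse events reported during the study. Its attribution paragraph has the investigator assign attribution after naming and grading the event.

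**When an adverse event begins.** Section 3.5.3 reads: "An adverse event is any undesirable sign, symptom or medical condition occurring after starting study drug (or therapy". No starting point is given for a patient assigned to observation. Pre-existing conditions are "only considered adverse events if they worsen after starting study treatment (any procedures specified in the protocol". Events between consent and the start of treatment are also recorded.

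**What observation patients do have.** One of the two serious-event windows in section 3.5.3 runs from consent to four weeks after study participation ends, so it covers both arms. The visit table schedules "Medical history", "Concurrent medications", examinations, vital signs and blood tests without an arm limit. The post-baseline lists in section 3.5.2 do not repeat history or medications.

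**Analysis.** Section 3.3.3 includes in the safety analysis any patient who took at least one dose. Sections 6.1.1 and 6.1.2 plan analyses of PFS and OS only, although section 3.5.3 expects toxicities to be reported with the trial results.

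**The concern.** A visit that assesses only treatment-related toxicity filters by attribution before grading. Section 3.5.3 sets the opposite order. A site designing its case report form cannot tell which rule governs.

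The control arm is observation and no placebo is described, so whoever judges relatedness knows the assignment. Section 3.3.2 requires every woman to have had both ovaries removed. Section 3.4 lists hot flashes, joint or muscle pain, trouble sleeping and tiredness among the effects of letrozole. It is clinical judgement, not a statement in the protocol, that such symptoms can arise without the drug in these women. If they do, and sites follow the visit schedule, the account of symptom tolerability rests on that judgement of relatedness. The trial's own randomised control group would not be there to show the background rate. Symptoms not graded at the visit are hard to reconstruct later.

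**Working it through.** The core of the point is textual. The arithmetic only sizes what could be gained.

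**1. Count of restricted assessments.** Visit table: 3 of 3 post-baseline toxicity cells carry the study-drug-arm footnote. Section 3.5.2: 3 of 3 post-baseline CTCAE items carry the same words. Because table and lists agree, a damaged table does not explain it. Between-arm safety comparisons in sections 6.1.1 and 6.1.2: 0.

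**2. Cover under each rule.**
- Letrozole, related event: covered by the schedule and by section 3.5.3.
- Letrozole, unrelated event: not in the schedule, but section 3.5.3 requires recording and grading.
- Observation, serious event: covered by the participation-based window.
- Observation, laboratory values, vital signs, examinations: scheduled without an arm limit.
- Observation, non-serious symptom: graded if reported as an adverse event, but no visit schedules it and the definition starts at a study drug or therapy that the patient never starts.

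Only the last line is a gap in collection. The second is a conflict of wording.

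**3. Visits affected.** Section 6.0 assumes a median PFS of 24 months under observation. 104 weeks / 12 = 8.7, so a patient who reaches it has 8 twelve-week visits.

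**4. Precision of a comparison.** Section 2.0 gives arthralgia of 21.2% with letrozole v 13.5% with tamoxifen in breast cancer, used here only as an illustration. The difference is 7.7 points. The 95% half-width is 1.96 × √(0.212×0.788/nL + 0.135×0.865/nO). Section 6.0 allows 10 to 80 patients with adaptive allocation, so the splits are assumptions:

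| Letrozole v observation | Half-width (points) | Interval (points) |
|---|---|---|
| 40 v 40 | 16.5 | −8.8 to 24.2 |
| 60 v 20 | 18.2 | −10.5 to 25.9 |
| 20 v 60 | 19.9 | −12.2 to 27.6 |

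**5. The same as a rate, on time at risk to first event.** Assume exponential times, median PFS of 24 months in both arms (h = ln 2/24 = 0.02888 per month) and a cut at T = 24 months. Incidence = λ/(λ+h) × (1 − exp(−(λ+h)T)). Solving for λ:
- 13.5% gives 0.00852 per month, or 10.2 per 100 patient-years.
- 21.2% gives 0.01417 per month, or 17.0 per 100 patient-years.

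With 40 per arm, patients with an event number 40×0.212 = 8.48 v 40×0.135 = 5.40, and time at risk is 49.9 v 52.8 patient-years. The difference is 6.8 per 100 patient-years, with half-width 196 × √(8.48/49.9² + 5.40/52.8²) = 14.3.

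**6. Why crude incidence alone would mislead.** Sections 3.4 and 3.6 end data collection at progression, so an arm with longer PFS is watched for longer. Hold the symptom rate equal in both arms, set observation to 13.5%, and assume a letrozole median PFS of 36 months. Crude letrozole incidence is then 14.9% with a cut at 24 months. With no cut, incidence is λ/(λ+h), with λ reset to give 13.5% under observation, and the letrozole figure is 19.0%. That is a 1.4 to 5.5 point difference with no drug effect on symptoms.

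**The case against.** The visit lists can be read as a scheduled minimum, with section 3.5.3 as the general rule. For dosed patients this stands: unrelated events must be recorded and graded, and only a visit prompt is missing. A reader might infer that unrelated events under letrozole go ungraded; the documents do not support that.

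A reader might also infer that section 3.3.3 shuts observation patients out of the safety analysis. It does not. It says dosed patients are included and is silent on others.

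The appended adverse event guidelines, which are not in the text available, may settle cover of the observation arm. The parenthesis about protocol procedures and the recording of events from consent may also extend it. This limits how firmly the gap can be stated, but it does not remove the printed restriction in sections 3.5.1 and 3.5.2.

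The trial is small, its objective is time to recurrence, and section 2.0 already reports controlled letrozole safety data from over 8,000 women. At 40 v 40 the power for a 7.7-point difference is about 15% (0.077/0.0842 = 0.91 standard errors). That stands against any formal test. It does not argue against describing symptoms in both arms at visits that both attend. The large trial compared letrozole with tamoxifen, not with observation after removal of the ovaries.

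**Conclusion.** The conflict is established: all scheduled post-baseline CTCAE assessments carry a limit by arm and by relatedness that section 3.5.3 does not. Its practical effect is narrow: no scheduled grading of non-serious symptoms in the observation arm, and no planned use of that arm to show background symptom rates. In the letrozole arm only the wording needs reconciling. It would go too far to say that safety under observation is not collected, since serious events, laboratory tests, vital signs and examinations are covered.

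PFS and OS conclusions are unaffected. The gain from closing the gap is descriptive, with an interval of about ±16.5 points at 40 v 40 and wider if allocation is unequal or the trial stops early. The figures rest on a tamoxifen comparator rate, assumed splits, exponential times and an assumed 36-month median in the follow-up example. The conclusion about the observation arm is subject to the appended guidelines. The change is worth making because it is cheap.

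**What to change.** - In the visit-table footnote and the three post-baseline lists, replace the limit with: all adverse events, CTCAE v3.0, both arms. Record attribution as a separate field for the letrozole arm.
- State in section 3.5.3 that the adverse event definition applies to both arms. Keep recording from consent, and count events from randomisation for the comparison.
- State that the safety summary includes observation patients as well as the dosed patients named in section 3.3.3.
- Report incidence and worst grade by randomised arm, with never-dosed letrozole patients identified. Add rates based on time at risk to first event and a 95% interval for the difference. Label the comparison descriptive.
- Check the appended guidelines for consistency.

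The cost is protocol and case report form wording, plus extra data entry at visits already scheduled; no visit or test is added. Reporting bias from known allocation remains.

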3.5.3. Safety assessments

Safety assessments will consist of monitoring and recording all adverse events and serious adverse events, the regular monitoring of hematology, blood chemistry and urine values, regular measurement of vital signs and the performance of physical examinations.

Adverse events

Information about all adverse events, whether volunteered by the subject, discovered by investigator questioning, or detected through physical examination, laboratory test or other means, will be collected and recorded. An adverse event is any undesirable sign, symptom or medical condition occurring after starting study drug (or therapy) even if the event is not considered to be related to study drug (or therapy). Study drug (or therapy) includes the drug (or therapy) under evaluation, and any reference or placebo drug (or therapy) given during any phase of the trial.

Medical conditions/diseases present before starting study treatment are only considered adverse events if they worsen after starting study treatment (any procedures specified in the protocol). Adverse events occurring before starting study treatment but after signing the informed consent form will also be recorded.

This study will utilize the Common Terminology Criteria for Adverse Events (CTCAE) version 3.0 for adverse event reporting. A copy of the CTCAE version 3.0 can be downloaded from the CTEP home page (http://www.ctep.info.nih.gov/) and is appended to this protocol. Life-threatening toxicities should be reported immediately to the Study Chairman, who in turn must notify the IRB. Reporting of adverse reactions is in addition to and does not supplant the reporting of toxicities as part of the results of the clinical trial.

This protocol will follow the Guidelines for Adverse Event Reporting appended to this protocol. In addition, the reporting requirements for Novartis are defined below.

Protocol Safety Requirements for Novartis

The principal investigator has the obligation to report all serious adverse events to the FDA, IRB, and Novartis Pharmaceuticals Clinical Safety and Epidemiology Department (CS&E).

Any Serious Adverse event occurring in a patient after providing informed consent, while receiving study drug, and until four weeks after stopping study drug must be reported by FAX **Sector**) to Novartis Pharmaceuticals CS&E Department within 24 hours of learning of it's occurrence, even if it is not felt to be drug related. It is requested that SAEs are reported to Novartis using the Norvartis SAE form (Appendix E)

Serious adverse events

A serious adverse event is an undesirable sign, symptom or medical condition which:

- 1. is fatal or life-threatening
- 2. required or prolonged hospitalization
- 3. results in persistent or significant disability/incapacity
- 4. constitutes a congenital anomaly or a birth defect
- 5. are medically significant, may jeopardize the subject and may require medical or surgical intervention to prevent one of the outcomes listed above.

Any serious adverse event occurring after the patient has provided informed consent and until 4 weeks after the patient has stopped study participation must be reported.

Grading/Rating Scale

- All adverse events reported during the study will be evaluated and graded on a scale of 1-5. The NCI Common Terminology Criteria for Adverse Events, v3.0 (CTCAE) will be used to determine the grade for all toxicities.
- 2. For any adverse events, which are not listed in the CTCAE the following rating system, will be used:

Grade Description

- 0 No AE or within normal limits
- 1 Mild AE (minor; no specific medical intervention; asymptomatic laboratory findings only, radiographic findings only; marginal clinical relevance)
- 2 Moderate AE (minimal intervention; local intervention; noninvasive intervention [packing, cautery])
- 3 Severe and undesirable AE (significant symptoms requiring hospitalization or invasive intervention; transfusion; elective interventional radiological procedure; therapeutic endoscopy or operation)
- 4 Life-threatening or disabling AE (complicated by acute, life-threatening metabolic or cardiovascular complications such as circulatory failure, hemorrhage, sepsis. Life-threatening physiologic consequences; need for intensive care or emergent invasive procedure; emergent interventional radiological procedure, therapeutic endoscopy or operation)
- 5 Fatal AE

Attribution is the determination of whether an AE is related to medical treatment or procedure. CTCAE does not define an AE as necessarily 'caused by a therapeutic intervention.' The clinical investigator must assign attribution for an adverse event after naming and grading of the event.

Attribution	Description
Unrelated	The AE is clearly NOT related to the intervention
Unlikely	The AE is doubtfully related to the intervention
Possible	The AE may be related to the intervention
Probable	The AE is likely related to the intervention
Definite	The AE is clearly related to the intervention

3.5.4. Drug levels and pharmacokinetic assessments

Drug levels/pharmacokinetic assessments will not be performed

3.6 Efficacy Assessment

Patients receiving letrozole will continue until progression or drug related toxicity. Those assigned to the observation group will be followed until disease progression. Progression will be defined as appearance of one or more new lesions on clinical exam or on radiologic imaging. At the physician's discretion, clinical findings can warrant further radiologic imaging. If the imaging reveals a new lesion, recurrent disease should be biopsy proven.

4.0 Protocol amendments

Any changes to the protocol will be made in the form of an amendment and will be approved by Novartis and the MD Anderson Cancer Center Institutional Review Board. Changes in study conduct are not permitted. Any unforeseen changes in study conduct will be recorded per institutional policy.

5.0 Data management

Registration:

This is a randomized, phase II trial of letrozole verses observation for patients with newly diagnosed, stage I and II, uterine leiomyosarcoma. All patients who meet eligibility criteria and are enrolled in this trial will be registered in Clinical Oncology Research Database (CORe) at the University of Texas MD. Anderson Cancer Center. The date in the current informed consent document is displayed to ensure only the most current IRB approved version is used. Consent date, registration date, off study date, and evaluability data are required for all registrants.

Data Collection:

Data will be collected and stored in the MD Anderson Protocol Data Management System (PDMS). Reporting to the sponsor, if applicable, will follow the contract agreement.

6.0 Statistical Design

We will accrue a minimum of 10 patients and a maximum of 80 patients at a rate of 2 patients per month. The primary outcome for this trial is the time to progression or death. Patients treated with standard of care (observation) have median progression-free survival (PFS) of 24 months [10]. We will follow all patients for at least 24 months following treatment.

Patients will be randomized between observation and letrozole using a Bayesian adaptive algorithm [22]. Details of this methodology are given in the "Technical Details" section below. The first 10 patients will be randomized fairly between the 2 treatment arms. After 10 patients are enrolled there will be 5 patients on each treatment arm. As the trial progresses and data accrue the randomization will become unbalanced in favor of the treatment that, on average, has better results in terms of PFS, so that each successive patient is more likely to receive the treatment showing better results.

The trial will be stopped early and a treatment selected as being "better" if the probability is 0.90 or more that one treatment's PFS is longer than the other treatment's PFS. However, if all 80 patients are enrolled, then a treatment will be selected as being "better" if the probability is 0.80 or more that one treatment's PFS is longer than the other treatment's PFS.

The operating characteristics of this study design are summarized in Table 1. These operating characteristics are based on 1000 simulations of the study design for 6 possible scenarios.

6.1 Outcomes

6.1.1 Primary Outcome

We will report the posterior probability that the letrozole arm has longer PFS than the observation arm. We will also provide a 95% posterior credible interval for the probability that the letrozole arm has longer PFS than the observation arm.

We will estimate the PFS with the Kaplan-Meier 23 product-limit estimator for each arm, and we will compare the PFS between the 2 arms with the log-rank test. We will model PFS with the Cox [24] proportional hazards regression model to estimate the hazard ratio for treatment (letrozole : observation), and we will construct the 95% confidence interval for this hazard ratio.

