6.2 Technical Details

Let MO and ML be the median PFS for treatments "observation" (O) and "letrozole" (L), respectively. We assume that MO and ML each have an inverse gamma prior distribution with mean 24 months and variance 57.6 months. The middle 95% of this prior distribution is between 13.4 and 42.6 months.

For each patient, the randomization probability for treatment O will be the posterior probability that it has the longer PFS, that is pO(data) = Pr(MO > ML| data) and the randomization probability for treatment L is pL(data) = 1 - pO(data). If at any point during the trial pL(data) > 0.90 (< 0.10) the trial will be terminated and treatment L will

be selected as superior (inferior). If the maximum number of patients is enrolled in the trial and pL(data) > 0.80 (< 0.20) treatment L will be selected as superior (inferior). If at any time during the trial we find that Pr(MO > 24 | data) < 0.05 or Pr(ML > 24 | data) < 0.05 we will suspend accrual to arm O or L, respectively, until this probability is 0.05 or greater.

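### Section 6.1.1 promises a 95% credible interval for a posterior probability that is one fixed number given the data, and plans no Bayesian interval for the size of the PFS effect

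*Combined protocol and SAP*

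**What the plan says.** Section 6.1.1 (Primary Outcome) plans two Bayesian items. The first is: "We will report the posterior probability that the letrozole arm has longer PFS than the observation arm". The second follows directly and uses the same words for its target: "We will also provide a 95% posterior credible interval for the probability that the letrozole arm has longer PFS than the observation arm". The section then plans Kaplan-Meier curves, a log-rank test and a Cox model, for which "we will construct the 95% confidence interval for this hazard ratio".

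Section 6.2 (Technical Details) takes MO and ML as the median PFS on observation and letrozole, and states that "MO and ML each have an inverse gamma prior distribution with mean 24 months and variance 57.6 months". It sets the randomization probability for observation to "the posterior probability that it has the longer PFS, that is pO(data) = Pr(MO > ML| data"), and the letrozole probability pL(data) to one minus that. The same pL(data) drives stopping: "If at any point during the trial pL(data) > 0.90 (< 0.10) the trial will be terminated". At full enrolment it is compared with 0.80 and 0.20 for selection. No section plans a credible interval for MO, ML, their ratio or their difference.

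**The concern.** A credible interval describes uncertainty about an unknown parameter. pL(data) is not a parameter. It is the posterior mass on one side of the line ML = MO, and it is fully determined once the data and the prior are given. As written, the promised interval has nothing to describe.

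Two things follow. First, a prespecified part of the primary report cannot be delivered, so the analyst must drop it or choose a substitute after seeing the data. Second, the Bayesian report is left with a statement of direction only. pL says how sure we are that letrozole is better, but not by how much. The Cox hazard ratio gives a size, but without the prior that enters every allocation and stopping decision. The two sizes can differ, most of all if the trial stops early with few events.

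**Working it through.** **1. The prior, checked against the plan's own figure.** The inputs are mean 24 and variance 57.6 (Section 6.2). For an inverse gamma:

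- shape = mean²/variance + 2 = 576/57.6 + 2 = 12
- scale = mean × (shape − 1) = 24 × 11 = 264

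The 2.5% and 97.5% points of IG(12, 264) are 13.41 and 42.58 months. Section 6.2 states 13.4 to 42.6, so the prior is reproduced.

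**2. Does pL(data) have a posterior distribution?** By definition pL(data) = Pr(ML > MO | data), which integrates over both medians. The only random quantity behind it is the 0/1 event that ML exceeds MO. That event equals 1 with probability pL and 0 with probability 1 − pL. Whenever pL lies between 0.025 and 0.975, its 2.5% point is 0 and its 97.5% point is 1. This was confirmed for no data (pL = 0.500) and for three assumed data sets (pL = 0.588, 0.797 and 0.902): the limits were 0 and 1 every time. An interval for simulation error around pL could be computed, but it would not be a posterior credible interval.

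**3. What the missing intervals would show.** The documents name no likelihood, so exponential PFS is assumed here. With d events over T patient-months in an arm, the posterior of its median is IG(12 + d, 264 + ln2 × T). The prior therefore counts like 12 events per arm. With posterior shapes aO, aL and scales bO, bL, the ratio ML/MO is distributed as k × F(2aO, 2aL), where k = (bL/bO)(aO/aL). Then pL = Pr(F > 1/k).

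Take equal events per arm, set the observation data to a 24-month median (TO = 24d/ln2), and solve for the TL that gives pL = 0.90 exactly. With equal shapes the posterior median of ML/MO is bL/bO.

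- d = 10: TO = 346.2 and TL = 692.9 patient-months. bO = 264 + 240 = 504.0 and bL = 264 + 480.3 = 744.3, so the ratio is 744.3/504.0 = 1.48.
- d = 30: TO = 1,038.7 and TL = 1,499.2. bO = 264 + 720 = 984.0 and bL = 264 + 1,039.2 = 1,303.2, so the ratio is 1,303.2/984.0 = 1.32.

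The prior-free hazard ratio, standing in for the Cox estimate, is TO/TL with log standard error √(2/d). For d = 10 this is 346.2/692.9 = 0.50, with limits 0.50 × exp(±1.96 × 0.447).

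| | 10 events per arm | 30 events per arm |
|---|---|---|
| pL | 0.90 | 0.90 |
| ML/MO (95% credible interval) | 1.48 (0.81 to 2.69) | 1.32 (0.86 to 2.04) |
| ML − MO, months | 10.9 (about −6 to 32) | 7.6 (about −4 to 21) |
| MO/ML, posterior | 0.68 (0.37 to 1.23) | 0.76 (0.49 to 1.16) |
| Hazard ratio, no prior (95% confidence interval) | 0.50 (0.21 to 1.20) | 0.69 (0.42 to 1.15) |

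The same pL goes with different effect sizes. The Bayesian and prior-free sizes differ more at 10 events (0.68 against 0.50) than at 30 (0.76 against 0.69).

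**4. At full enrolment.** Further assumptions are true medians of 24 and 36 months, 80 patients accrued at 2 per month over 40 months, expected data at month 64, allocation 40/40 and no early stop. The expected data are 28.3 events over 980 patient-months on observation and 22.6 over 1,174 on letrozole. These give pL = 0.89, ML/MO = 1.33 (0.85 to 2.11) and ML − MO = 7.8 months (−4.6 to 22.4). This pL passes the 0.80 selection threshold, yet the size of effect under the model remains wide. Under the plan as written, that width would not be reported.

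**The case against.** The strongest objection is that nothing turns on the sentence. Randomization, stopping, selection and arm suspension all use posterior probabilities as single numbers, so deleting the sentence would change no decision. An effect size with uncertainty is already planned through the Cox model, and the documents never promise a Bayesian one. In both rows of figures above, the credible and confidence intervals include 1 and point the same way. All of this stands, and it limits the finding to reporting.

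A second objection is that the target may be misnamed and not impossible. The authors may have meant the chance that a letrozole patient outlasts an observation patient. Under exponential PFS that is ML/(ML + MO), a function of the parameters with a valid credible interval: 0.42 to 0.68 for an assumed 15 events in 480 patient-months on observation and 15 in 700 on letrozole. But the documents define this quantity nowhere, and Section 6.1.1 uses identical wording for the posterior probability one sentence earlier. If it was meant, the text still needs correcting.

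Third, the illustrations measure the weight of the prior and not the wording error, and they depend on an assumed likelihood and, in step 4, on fixed equal allocation in an adaptive trial. This is fair. They show why a Bayesian size is worth reporting and should not be read as the size of the error.

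**Conclusion.** The concern holds. Under Section 6.2 the promised interval is undefined, and no credible interval is planned for any quantity that could have one. That conclusion follows from the definitions alone and needs no distributional assumption. The error itself has no numerical size and does not affect the conduct or decisions of the trial.

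The practical loss is that effect size under the model that runs the trial goes unreported. Assuming exponential PFS and equal events per arm, pL = 0.90 can accompany a posterior ML/MO of 1.48 or 1.32, and the posterior MO/ML differs from the prior-free hazard ratio by 0.18 (0.68 − 0.50) at 10 events per arm and by 0.07 (0.76 − 0.69) at 30. The correction should be made because the item belongs to the primary outcome report, but it is not a threat to the design.

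**What to change.** In Section 6.1.1, replace the sentence on the credible interval with:

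*We will give pL(data) as one number, together with the posterior median and 95% credible interval of ML/MO, ML − MO, MO and ML, calculated from the posteriors used for the randomization.*

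Keep the Cox hazard ratio and its 95% confidence interval as planned. If the authors intended a patient-level probability, they should define it explicitly as a function of the model parameters and state its interval as an addition.

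The cost is one sentence. The posteriors are already computed for the randomization, and no design feature, sample size or decision rule changes.
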